## 1.2. GS-7977

GS-7977 is a nucleotide analog that is a potent and selective inhibitor of NS5B-directed HCV replication.

Please refer to the Investigator's Brochure (IB) for additional information on GS-7977 including:

- In Vitro Anti-HCV Activity
- Nonclinical Pharmacokinetics and In Vitro Metabolism
- Nonclinical Pharmacology and Toxicology
- Clinical Experience

## 1.3. Summary of Additional Clinical Experience

GS-7977 is being studied in combination with PEG, RBV, and other direct acting antivirals (DAAs) for the treatment of chronic HCV infection. There is an ongoing clinical pharmacology program and there are later stage studies in all genotypes. Additional drug interactions studies with key HIV antiretrovirals (ARVs) are also discussed as they are relevant to the study population of this protocol. GS-US-334-0131 evaluated GS-7977-ARV DDIs in healthy volunteers and P7977-1910 evaluated GS-7977-ARV DDIs and viral kinetics in HIV/HCV coinfecting subjects.

### 1.3.1. GS-US-334-0131

This open-label, multiple-dose, fixed-sequence, five-cohort, single-center study was conducted in healthy volunteers and evaluated the potential for drug-drug interaction between GS-7977 and HIV medications Atripla®, Darunavir (DRV) /r, Raltegravir (RAL) and Rilpivirine (RPV). Seventy-four evaluable subjects comprised of male and non-pregnant, non-lactating female subjects between 18 and 45 years old were enrolled into one of four cohorts and received study treatments as follows:

#### Cohort 1 (under fasted conditions)

Days			
1	2-4	5-18	19
GS-7977 (400 mg tablet) single dose in the AM	Washout	Atripla® EFV/FTC/TDF ( 600/200/300 mg tablet, QD) in the AM	GS-7977 (400 mg tablet) single dose in the AM PLUS Atripla® EFV/FTC/TDF (600/200/300 mg tablet, QD) in the AM

**Cohort 2 (under fed conditions)**

Days			
1	2-4	5-14	15
GS-7977 (400 mg tablet) single dose in the AM	Washout	Darunavir/ritonavir; DRV/r; (800/100 mg tablet QD) in the AM	GS-7977 (400 mg tablet) single dose in the AM PLUS DRV/r; (800/100 mg tablet QD) in the AM

**Cohort 3 (under fasted conditions)**

Days			
1	2-4	5-14	15
GS-7977 (400 mg tablet) single dose in the AM	Washout	AM/PM dose: Raltegravir; RAL (400 mg tablet, AM/PM dose)	GS-7977 (400 mg tablet) single dose in the AM PLUS RAL (400 mg tablet, AM dose only)

**Cohort 4 (under fed conditions)**

Days			
1	2-4	5-14	15
GS-7977 (400 mg tablet) single dose in the AM	Washout	Rilpivirine; RPV (25 mg tablet, QD) in the AM	GS-7977 (400 mg tablet) single dose in the AM PLUS RPV (25 mg tablet, QD) in the AM

1.3.1.1. GS-US-334-0131 Preliminary Pharmacokinetic Analysis

Serial blood samples for PK analyses were collected on Day 1 (post GS-7977 dose) and Days 14-19 (HIV medication alone or in combination with GS-7977) at selected timepoints. The study conduct is completed and preliminary pharmacokinetic analyses have been completed. Results from Cohorts 1 to 4 are presented below.

**Table 1-1. GS-US-334-0131: Cohort 1 Preliminary Pharmacokinetic Analysis**

Cohort 1: Sixteen subjects completed the study procedures and the data are as follows:

Effect of ATR (EFV/FTC /TDF) on GS-7977 (n=16)			
GS-7977			
Mean (%CV)	GS-7977 alone	GS-7977 + ATR	%GMR (90%CI)
AUC inf (ng.hr/ml)	827 (41.7)	777 (41.1)	93.9 (75.9-116)
C max (ng/ml)	1020 (47.7)	877 (64.0)	80.9 (59.6-110)
GS-566500			
Mean (%CV)	GS-7977 alone	GS-7977 + ATR	%GMR (90%CI)
AUC inf (ng.hr/ml)	1140 (27.8)	895 (28.2)	79.2 (69.4-90.4)
C max (ng/ml)	308 (37.5)	218 (37.2)	72.1 (62.2-83.7)
GS-331007			
Mean (%CV)	GS-7977 alone	GS-7977 + ATR	%GMR (90%CI)
AUC inf (ng.hr/ml)	11,300 (19.0)	9,620 (25.7)	84.0 (76.2-92.5)
C max (ng/ml)	1,250 (24.2)	965 (26.8)	76.7 (69.8-84.3)
Effect of GS-7977 on ATR (EFV/FTC/TDF) (n=16)			
TDF			
Mean (%CV)	ATR alone	ATR + GS-7977	%GMR (90%CI)
AUC tau (ng.hr/ml)	2,270 (22.6)	2,210 (20.3)	97.7 (91.1-105)
C max (ng/ml)	274 (32.0)	343 (29.6)	125 (108-145)
C trough (ng/ml)	43.7 (23.1)	42.9 (20.6)	98.6 (91.3-106)
FTC			
Mean (%CV)	ATR alone	ATR + GS-7977	%GMR (90%CI)
AUC tau (ng.hr/ml)	9,910 (17.6)	9,810 (17.2)	99.1 (93.7-105)
C max (ng/ml)	1,840 (28.6)	1,780 (27.2)	96.9 (87.6-107)
C trough (ng/ml)	69.2 (22.0)	73.0 (25.6)	104 (97.6-111)
EFV			
Mean (%CV)	ATR alone	ATR + GS-7977	%GMR (90%CI)
AUC tau (ng.hr/ml)	70,900 (56.2)	69,600 (62.7)	96.7 (90.8-103)
C max (ng/ml)	4,410 (45.2)	4,250 (50.7)	94.7 (84.6-106)
C trough (ng/ml)	2,310 (68.0)	2,280 (75.4)	96.9 (94.0-99.8)

Modest decreases in systemic exposure of GS-7977 and GS-566500 (GS-56500 Cmax decreased by 28%) with no effect on GS-331007 were noted on co-administration of GS-7977 with ATR. TDF, FTC and EFV PK were unaltered by GS-7977, with the exception

of a slight increase in TDF Cmax (25%) that is not considered to be clinically significant. Based on these results, GS-7977 can be co-administered with ATR or its components (TDF, FTC, FTC/TDF and EFV).

**Table 1-2. GS-US-334-0131: Cohort 2 Preliminary Pharmacokinetic Analysis**

Cohort 2: Eighteen subjects completed the study procedures and the data are as follows:

Effect of DRV/r on GS-7977 (n=18)			
GS-7977			
Mean (%CV)	GS-7977 alone	GS-7977 + DRV/r	%GMR (90%CI)
AUCinf (ng.hr/ml)	1,130 (47.7)	1,330 (30.6)	133 (112-157)
Cmax (ng/ml)	544 (48.3)	773 (55.8)	145 (110-192)
GS-566500			
Mean (%CV)	GS-7977 alone	GS-7977 + DRV/r	%GMR (90%CI)
AUCinf (ng.hr/ml)	1,410 (36.8)	2,430 (29.4)	180 (163-198)
Cmax (ng/ml)	266 (38.4)	468 (34.9)	180 (156-208)
GS-331007			
Mean (%CV)	GS-7977 alone	GS-7977 + DRV/r	%GMR (90%CI)
AUCinf (ng.hr/ml)	11,900 (16.0)	14,700 (16.7)	124 (117-130)
Cmax (ng/ml)	1,020 (20.7)	988 (19.8)	97.3 (90.1-105)
Effect of GS-7977 on DRV/r: Cohort 2, fed (n=18)			
DRV			
Mean (%CV)	DRV/r alone	DRV/r + GS-7977	%GMR (90%CI)
AUCtau (ng.hr/ml)	116,000 (25.8)	113,000 (26.2)	97.0 (94.2-99.8)
Cmax (ng/ml)	9,740 (20.3)	9,480 (19.8)	97.3 (94.1-101)
Ctrough (ng/ml)	3,330 (40.4)	2,860 (38.6)	98.6 (91.3-106)
RTV			
Mean (%CV)	DRV/r alone	DRV/r + GS-7977	%GMR (90%CI)
AUCtau (ng.hr/ml)	4,400 (45.2)	4,220 (46.4)	94.9 (88.1-102)
Cmax (ng/ml)	630 (50.2)	608 (46.4)	94.8 (84.3-107)
Ctrough (ng/ml)	45.8 (51.5)	42.1 (54.9)	91.4 (86.1-97.0)

DRV/r increased GS-7977 and GS-566500 systemic exposure (33 to 80% respectively) but did not substantially alter the PK of GS-331007 (AUC: 24 % increase). The PK of DRV and RTV was unchanged on administration of GS-7977. The increase in GS-7977 exposure on

administration with DRV/r does not necessitate dose adjustment (based on results from P7977-1918). GS-7977 can be co-administered with DRV/r.

**Table 1-3. GS-US-334-0131: Cohort 3 Preliminary Pharmacokinetic Analysis**

Cohort 3: Eighteen subjects completed the study procedures and the data are as follows:

Effect of RAL on GS-7977 (n=18)			
GS-7977			
Mean (%CV)	GS-7977 alone	GS-7977 + RAL	%GMR (90%CI)
AUC inf (ng.hr/ml)	876 (50.9)	1,380 (75.8)	143 (104-197)
C max (ng/ml)	943 (58.5)	807 (45.1)	87.3 (70.7-108)
GS-566500			
Mean (%CV)	GS-7977 alone	GS-7977 + RAL	%GMR (90%CI)
AUC inf (ng.hr/ml)	1,160 (27.5)	1,180 (33.0)	99.6 (87.7-113)
C max (ng/ml)	316 (29.2)	285 (30.2)	88.9 (78.7-100)
GS-331007			
Mean (%CV)	GS-7977 alone	GS-7977 +RAL	%GMR (90%CI)
AUC inf (ng.hr/ml)	11,200 (21.6)	11,500 (20.7)	103 (97.3-109)
C max (ng/ml)	1,100 (22.6)	1,190 (22.3)	109 (98.9-120)
Effect of GS-7977 on RAL (n=18)			
Mean (%CV)	RAL alone	RAL + GS-7977	%GMR (90%CI)
AUC tau (ng.hr/ml)	6,480 (74.6)	5,790 (100)	73.1 (58.6-91.1)
C max (ng/ml)	2,350 (83.9)	1,840 (113)	57.4 (43.7-75.4)
C trough (ng/ml)	66.6 (51.0)	61.7 (45.6)	95.0 (81.0-112)

GS-7977 AUCinf was 43% higher in the presence of RAL. The PK of both GS-7977 metabolites (GS-566500 and GS-331007) was unchanged by RAL. As described earlier (results from P7977-1918), the increase in GS-7977 AUC is not considered to be clinically relevant.

GS-7977 decreased RAL AUCtau and Cmax (~27 and 43% respectively) but did not alter RAL trough concentrations. The RAL prescribing information states that no dose adjustment for RAL is required on dosing with tipranavir/r which decreases RAL exposure comparable to

values seen in this study. Based on the prescribing label and considering that dosing with GS-7977 did not alter RAL trough concentrations, GS-7977 may be co-administered with RAL, 400 mg BID.

**Table 1-4. GS-US-334-0131: Cohort 4 Preliminary Pharmacokinetic Analysis**

Cohort 4: Seventeen subjects completed the study procedures and the data are as follows:

Effect of RPV on GS-7977 (n=17)			
GS-7977			
Mean (%CV)	GS-7977 alone	GS-7977 + RPV	%GMR (90%CI)
AUC inf (ng.hr/ml)	847 (30.2)	944 (37.8)	109 (93.6-127)
C max (ng/ml)	463 (56.4)	587 (66.6)	120.6 (89.6-162)
GS-566500			
Mean (%CV)	GS-7977 alone	GS-7977 + RPV	%GMR (90%CI)
AUC inf (ng.hr/ml)	1,290 (25.9)	1,260 (26.4)	97.6 (88.1-108)
C max (ng/ml)	256 (38.1)	263 (35.0)	103 (87.8-121)
GS-331007			
Mean (%CV)	GS-7977 alone	GS-7977 +RPV	%GMR (90%CI)
AUC inf (ng.hr/ml)	11,400 (18.6)	11,500 (19.2)	100 (96.6-104)
C max (ng/ml)	1,000 (22.1)	1,060 (22.2)	106 (98.6-114)
RPV (n=17)			
Mean (%CV)	RPV alone	RPV + GS-7977	%GMR (90%CI)
AUC tau (ng.hr/ml)	2,770 (36.7)	2,930 (37.1)	105 (102-109)
C max (ng/ml)	195 (28.8)	210 (35.5)	105 (96.6-115)
C trough (ng/ml)	109 (43.1)	109 (45.8)	98.9 (94.4-103)

GS-7977 and RPV are not involved in a clinically relevant drug interaction (20% increase in GS-7977 Cmax). GS-7977 can be co-administered with RPV.

Conclusions: There were no clinically significant drug-drug interactions observed between GS-7977 and the HIV ARVs EFV, FTC/TDF, DRV/r, RAL or RPV. These data support potential use of GS-7977 with a variety of ARV regimens in the HIV/HCV co-infected population.

### 1.3.1.2. GS-US-334-0131 Preliminary Safety

Preliminary safety was evaluated in this population where both ARV medications and GS-7977 are considered study drugs. There were a total 65 adverse events in 33 patients, the majority of which were related to study procedure or study medication. The most frequent adverse events were dizziness, headache, diarrhea, nausea and constipation with the majority occurring in the Cohort 1 (Atripla) subjects. All events were mild with the exception of a single case of facial pain graded, unrelated to study drug, graded as moderate. The majority of these events occurred during ARV medication dosing, predominantly in Cohort 1 (Atripla), and were consistent with known early toxicities of EFV. Few events were treatment-emergent during the administration of GS-7977. No Grade 3 or 4 laboratory abnormalities observed during the study period.

[figure not shown]
### 1.3.2. P7977-1910

This study is an open-label, single sequence design conducted in approximately 40 evaluable healthy HIV/HCV co-infected subjects to evaluate the pharmacokinetic interactions between GS-7977 and EFV + TDF + FTC, EFV + ZDV + 3TC, ATV/r + TDF + FTC, DRV/r + TDF + FTC, and RAL. The study consisted of 5 cohorts of 8 co-infected subjects that are using one of the above ARV combinations for a minimum of 4 weeks prior to GS-7977 dosing. Subjects were maintained on a similar timing and dosing conditions for taking their ARV regimens during the study period as taken prior to the study. During the treatment period subjects received GS-7977 in combination with one of the above regimens for 7 days. Blood samples for pharmacokinetic analysis of each ARV component were collected serially throughout the dosing interval on the day prior to initiation of GS-7977 treatment and final day of co-administration with GS-7977. GS-7977 and its metabolites, GS-352707 and GS-6206, plasma concentrations were obtained on the final day of co-administration with ARV. HIV and HCV RNA samples were collected at baseline, throughout co-administration of GS-7977 and ARV and during follow-up. The study conduct is ongoing but preliminary safety and antiviral activity is available for the first 30 subjects.

#### 1.3.2.1. Preliminary Viral Kinetics

[figure not shown]
A total of 30 subjects have been enrolled to date across the 5 cohorts. All subjects were on stable ARV regimen with undetectable HIV RNA, and CD4 >350 cells/mm^3 were enrolled. There were 6 adverse events observed in 5 subjects, none of which were identified as related to study drug. Median change in HCV RNA was similar for all 5 groups during the 7-day dosing period, with >1.5 log10 reductions at 24 hours and a maximal HCV RNA decline from baseline >4 log10. Virologic response was similar across all 5 cohorts independent of HCV genotype, and baseline HCV viral load.

**Figure 1-1. GS-7977 Activity in HIV/HCV Coinfection**

Additionally, patient characteristics and median HCV RNA log10 change from baseline were compared with results from two prior HCV monoinfected cohorts in HCV genotype (GT) 1 and GT 2/3 patients (Figure 1-2). Virologic response was similar across all 5 cohorts independent of HIV status, HCV genotype, and baseline HCV viral load. Comparable HCV early viral kinetics was observed in HIV/HCV coinfecting and HCV monoinfected patients, supporting further study of GS-7977 in HIV/HCV coinfecting patients.

**Figure 1-2. Comparative GS-7977 Antiviral Activity in HCV Monoinfection vs HIV/HCV Coinfection**

1.3.2.2. Preliminary Safety

GS-7977 has been safe and well tolerated in the study population. No new safety signals were observed during the study period or safety follow-up. Three subjects experienced CNS side-effects who were erroneously dosed with Atripla 12 hours apart on Day-1, all of which resolved with standard daily dosing of Atripla. Other adverse events reported included headache, nausea, dry mouth, and chills, all of which were mild and not related to study drug. No SAEs or deaths have occurred in the study population. No effect was observed on HIV viral load, CD4 count, or CD4%.

1.3.2.3. Preliminary Pharmacokinetics

Preliminary pharmacokinetic results are available for 8 and 2 subjects, respectively, receiving ATV/r and GS-7977 in cohort 3 (ATV/r+TDF+FTC).

Cohort 3 (ATV/r+TDF+FTC)				
Mean (%CV)		Day 0	Day 7	%GMR (90%CI)
ATV (n=8)	AUC tau (ng*hr/ml)	49,600 (32.9)	52,500 (43.8)	100.5 (80.51, 125.4)
	C max (ng/ml)	4930 (40.5)	4620 (43.9)	91.63 (76.39, 109.9)
	C tau (ng/ml)	817 (35.9)	1103 (56.5)	122.5 (90.57, 165.7)
RTV (n=8)	AUC tau (ng*hr/ml)	11,400 (41.2)	8,750 (30.6)	79.05 (64.63, 96.70)
	C max (ng/ml)	1600 (42.7)	1050 (31.5)	67.93 (52.81, 87.37)
	C tau (ng/ml)	82.7 (39.8)	84.3 (59.9)	98.13 (75.36, 127.8)

Cohort 3 (ATV/r+TDF+FTC)				
		Day 7 (Range of n=2)	P2938-0212 Mean (%CV), (n=8)	Day 7 / P2938-0212 (Range of n=2)
GS-7977	AUC tau (ng*hr/ml)	2510 - 2750	538 (39.0)	4.7 – 5.1
	C max (ng/ml)	1210 - 1930	603 (47.2)	2.0 – 3.2
GS-566500	AUC tau (ng*hr/ml)	3,650 - 20,600	853 (45.7)	4.3 – 24.2
	C max (ng/ml)	673 - 4,150	235 (38.4)	2.9 – 17.7
GS-331007	AUC tau (ng*hr/ml)	16,200 - 16,500	9640 (18.7)	1.7 – 1.7
	C max (ng/ml)	984 - 1470	1380 (19.2)	0.71 – 1.1

As reflected in the GMR (90% CI), co-administration of GS-7977 did not alter ATV AUCtau or Cmax, and modestly increased ATV Ctau (23%). ATV exposures achieved in this study were comparable to historical data in HIV-infected patients (Reyataz® prescribing information for ATV/r 300/100). Reyataz® prescribing information for ATV/r 300/100). The effect of GS-7977 on ritonavir pharmacokinetics was also fairly modest; ritonavir AUCtau and Cmax were decreased 21% and 32% respectively, but Ctau was not affected by GS-7977.

Exposures (AUC) were higher for GS-7977 (4.7-5.1-fold), GS-566500 (4.3-24-fold) and GS-331007 (1.7-fold) upon co-administration of GS-7977 and ATV/r, as compared to exposures achieved following administration of GS-7977 400 mg alone for 7 days in a previous study (study P2938-0212). Of note, the exposure (AUC) of GS-7977 and GS-331007 within this dataset is similar to values seen in other clinical trials including drug-drug interaction, thorough QT, safety, efficacy, and special population studies. The PK of the intermediate metabolite GS-566500 was highly variable and should be interpreted with caution.

The higher GS-7977 exposure is not considered clinically significant due to its very low and transient exposure relative to total drug related material (DRM) exposure (DRM, calculated

as the sum of the AUCs for each of the analytes, corrected for molecular weight). Based on this calculation, the AUC of GS-7977 with ATV/r is ~ 4.4% to 6.2% of DRM AUC. In a previous drug-drug interaction study (P7977-1819), the AUC of GS-7977 increased from ~3 % (GS-7977 alone) to ~11% (GS-7977 with cyclosporine) of DRM AUC upon co-administration of GS-7977 with cyclosporine, a potent multi-drug transporter inhibitor. Safety margins for GS-7977 and GS-331007 on administration with cyclosporine are adequate (AUC safety margin ranges from 1.3 to 13.6) compared to exposures obtained in toxicology studies and dose modification of GS-7977 is not warranted.

### 1.3.3. Study P7977-0523 (ELECTRON): additional efficacy data

This ongoing Phase 2a, 4-part, 13-group study evaluated GS-7977 400 mg for 8 or 12 weeks in combination with or without RBV and/or PEG in subjects with genotypes 1, 2, or 3 HCV infection and with or without GS-5885 or GS-9669 in subjects with genotype 1 HCV infection. Preliminary HCV RNA data, including the 12 week posttreatment time point for all subjects in the first 9 groups, are tabulated in Table 1-5.

**Table 1-5. P7977-0523: Percentage of Subjects with HCV RNA Below the Lower Limit of Detection at Select Timepoints in Study**

Time (Week)	Genotype-2/3 Treatment Naive				Genotype 1 Null Responders	Genotype 1 Treatment Naive	Genotype 2/3 Treatment Experienced
	GS-7977+RBV 12 weeks (Group 1) (N = 10) n (%)	GS-7977+PEG+RBV 12 weeks (Groups 2,3,4) (N = 30) n (%)	GS-7977 12 weeks (Group 5) (N = 10) n (%)	GS-7977+PEG+RBV 8 weeks (Group 6) (N = 10) n (%)	GS-7977+RBV 12 weeks (Group 7) (N = 10) n (%)	GS-7977+RBV 12 weeks (Group 8) (N = 25) n (%)	GS-7977+RBV 12 weeks (Group 9) (N = 25) n (%)
0	0	0	0	0	0	0	0
1	2 (20.0)	8 (26.7)	5 (50.0)	6 (60.0)	1 (10.0)	8 (32.0)	8 (32.0)
2	8 (80.0)	23 (80.0)	8 (80.0)	10 (100.0)	7 (70.0)	17 (68.0)	21 (84.0)
3	9 (90.0)	25 (83.3)	10 (100.0)	10 (100.0)	10 (100.0)	22 (88.0)	25 (100.0)
4	10 (100.0)	30 (100.0)	10 (100.0)	10 (100.0)	10 (100.0)	25 (100.0)	25 (100.0)
EOT a	10 (100.0)	30 (100.0)	10 (100.0)	10 (100.0)	10 (100.0)	25 (100.0)	25 (100.0)
SVR4	10 (100.0)	30 (100.0)	6 (60.0)	10 (100.0)	1 (10.0)	22 (88.0)	19 (76.0)
SVR12	10 (100.0)	30 (100.0)	6 (60.0)	10 (100.0)	1 (10.0)	21 (84.0)	17 (68.0)

a EOT, End of Treatment

### 1.3.4. Study AI444-040 (Bristol-Myers Squibb IND 79,599)

AI444-040 {20485} was designed to evaluate the potential to achieve SVR with an oral, pan-genotypic, once-daily treatment regimen combining the investigational agents GS-7977

and a NS5A inhibitor, daclatasvir (DCV), with or without RBV, in treatment naïve patients chronically infected with genotypes 1, 2, or 3 HCV. In the initial phase of this study, patients were randomized into six groups, evaluating three different dosing schedules in patients with either genotype 1 HCV (n=44) or genotype 2/3 HCV (n=44). The groups were:

- GS-7977 400 mg QD for 7 days then DCV 60 mg QD + GS-7977 400 mg QD for 23 weeks
- GS-7977 400 mg QD + DCV 60 mg QD for 24 weeks
- GS-7977 400 mg QD + DCV 60 mg QD + ribavirin for 24 weeks

The primary endpoint of the study was SVR12. An interim analysis for safety and antiviral activity was conducted at 12 weeks on-treatment. An additional interim analysis for antiviral efficacy was conducted four weeks post-treatment.

The study was subsequently expanded to evaluate GS-7977 + DCV ± RBV for 24 Weeks in genotype 1 HCV infected patients who have previously failed TVR or BVR treatment and for 12 Weeks in treatment-naïve genotype 1 HCV patients. These treatment groups are currently under study.

#### 1.3.4.1. Study AI444-040 Preliminary Safety

Safety data from this ongoing study are available through 12 weeks on-treatment. The most frequent (greater than or equal to 15% overall) adverse events (AEs) on treatment were fatigue, headache and nausea. Adverse events were generally mild to moderate intensity and did not lead to treatment discontinuation. Grade 3-4 laboratory abnormalities included anemia, elevated glucose, elevated fasting glucose, lymphopenia and low serum phosphorus—all of which occurred in patients who received RBV. Grade 3-4 laboratory abnormalities reported in the RBV-sparing treatment groups were low phosphorus and elevated cholesterol. Two patients discontinued treatment for non-drug related AEs and both achieved SVR4. No patients discontinued therapy due to treatment-related AEs.

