- b) On a stable, protocol-approved, ARV for  $>8$  weeks prior to Screening with a CD4 T-cell count  $>200$  cells/mm^3 and a documented undetectable plasma HIV-1 RNA level for  $\geq 8$  weeks by local assay preceding the Screening visit. HIV-1 RNA levels should be measured within 1 year of the Screening visit. Screening HIV RNA must be  $< 50$  cp/mL as measured by the COBAS AMPLIPREP/COBAS TaqMan 2.0 HCV RNA assay.
- Subjects who switched from atazanavir/ritonavir (boosted) to darunavir/ritonavir (boosted) prior to Amendment 2 will be exempt from the 8 week stable ARV regimen requirement as defined in Section 6.4.2.
- c) HIV antiretroviral medications allowed in this study include the following and should be administered per the prescribing information in the package insert:
- emtricitabine/tenofovir plus:
    - atazanavir/ritonavir (boosted); or
    - darunavir/ritonavir (boosted); or

- efavirenz; or
- raltegravir; or
- rilpivirine

Alternative combinations of the above listed medications may be allowed on a case by case basis. ARV regimens not on the above list are excluded from this study.

10. Body mass index (BMI)  $\geq 18 \text{ kg/m}^2$
11. Screening ECG without clinically significant abnormalities as determined by the investigator
12. Subjects must have the following laboratory parameters at screening:
  - a) ALT  $\leq 10 \times$  the upper limit of normal (ULN)
  - b) AST  $\leq 10 \times$  ULN
  - c) Hemoglobin  $\geq 12 \text{ g/dL}$  for male,  $\geq 11 \text{ g/dL}$  for female subjects
  - d) INR  $\leq 1.5 \times$  ULN unless subject has known hemophilia or is stable on an anticoagulant regimen affecting INR
  - e) Albumin  $\geq 3 \text{ g/dL}$
  - f) Direct bilirubin  $\leq 1.5 \times$  ULN
    - For subjects receiving an atazanavir/ritonavir (boosted) regimen, a direct bilirubin  $> 1.5 \times$  ULN will be allowed if  $< 25\%$  of the total bilirubin.
  - g) HbA1c  $\leq 10\%$
  - h) Creatinine clearance ( $CL_{cr}$ )  $\geq 60 \text{ mL/min}$ , as calculated by the Cockcroft-Gault equation {2202}
13. Subject has not been treated with any investigational drug or device within 30 days of the Screening visit
14. A female subject is eligible to enter the study if it is confirmed that she is:
  - a. Not pregnant or nursing

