#### **6.4. Procedures and Specifications**

##### **6.4.1. Clinical Laboratory Analytes**

Hematology: Hematocrit, Hemoglobin (Hb), Platelet count, Red blood cell count (RBC), White blood cell count (WBC) with differential (absolute and percentage) including Lymphocytes, Monocytes, Neutrophils, Eosinophils, Basophils, Reticulocyte count and MCV.

Coagulation: INR, Prothrombin time (PT), Activated partial thromboplastin time (APTT)

Chemistry: Alanine aminotransferase (ALT/SGPT), Aspartate aminotransferase (AST/SGOT), Albumin, Alkaline phosphatase, Creatinine, Total Bilirubin (reflex to Direct Bilirubin), Glucose, Lipase, Potassium, Sodium, Fibrotest®, APRI, and Gamma-glutamyl transferase (GGT).

Urinalysis: Appearance, Blood, Color, Glucose, Leukocyte esterase, pH, Protein, Urobilinogen. Reflex to microscopic urinalysis if dipstick result is abnormal.

Virological Tests: Serologies for HCV, HBV and HIV. HCV RNA will be measured using the COBAS® TaqMan® HCV Test, v2.0 for Use with the High Pure System. HCV genotype and subtype will be determined using the Siemens VERSANT® HCV Genotype INNO-LiPA 2.0 Assay. HIV RNA will be measured using the AmpliPrep/COBAS® TaqMan® HIV-1 Test, v2.0. If HIV-1 virologic rebound is confirmed, HIV-1 genotype/phenotype will be determined using the PhenoSense™ Integrase HIV, GeneSeq™ Integrase HIV, PhenoSense™ HIV, GenoSure MG, GeneSeq™ HIV, and PhenoSense GT™. Gilead reserves the right to use alternate assays for HCV RNA, HIV RNA, HCV genotype, and HIV-1 genotype/phenotype should the above assays become unavailable.

IL28B genotype will be determined by polymerase chain reaction (PCR) amplification of the SNP, rs12979860, with sequence specific forward and reverse primers and allele specific fluorescently labeled TaqMan® MGB probes. Gilead reserves the right to use alternate assays for IL28B determination should the above assay become unavailable.

Pregnancy Tests: Serum  $\beta$ -hCG, Urine  $\beta$ -hCG (if positive, requires immediate confirmation with Serum  $\beta$ -hCG)

Pharmacokinetic Tests: The exact time of the dose taken prior to collection of the PK sample and the exact time the PK sample is drawn will be recorded on the appropriate eCRF. Information on food intake prior to dosing on days of PK assessments will be collected.

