Additional Tests: Urine Drug screen (for Amphetamines, Cocaine, Methadone, Opiates), Hemoglobin A1c (HbA1c). TSH (reflex T3 and T4). CD4 T-lymphocyte Absolute Count and %

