3.2	Forest Plot of SVR12 by Subgroup	Full Analysis Swet

Listing Number	Title	Analysis Set
1	Subject Disposition	Safety Analysis Set
2	Subject Demographics and Baseline Characteristics	Safety Analysis Set
3	Medical History	Safety Analysis Set
4	Study Drug Administration	Safety Analysis Set
5	Prior and Current HIV Medications	Safety Analysis Set
6	Subjects with HCV Virologic Failure	Full Analysis Set
7.1	HCV RNA (log10 IU/mL) and Change from Baseline for All Subjects in the FAS	Full Analysis Set
7.2	HCV RNA (log10 IU/mL) and Change from Baseline for All Subjects in the Safety Analysis Set but Not in FAS	Safety Analysis Set
8	All Adverse Events	Safety Analysis Set
9	Grade 3 or 4 Adverse Events	Safety Analysis Set

10	Adverse Events Leading to Permanent Discontinuation from Any of the Study Drugs	Safety Analysis Set
11	Adverse Events Leading to Permanent Discontinuation from SOF	Safety Analysis Set
12	Serious Adverse Events	Safety Analysis Set
13	Pregnancy	Safety Analysis Set
14	Deaths	Safety Analysis Set
15	Central Laboratory (Covance) Reference Ranges	Safety Analysis Set
16	Subjects with Treatment-Emergent Grade 3 or 4 Laboratory Abnormalities	Safety Analysis Set
17.1	Hematology: RBC, Reticulocyte Count, WBC, Lymphocytes, and Neutrophils	Safety Analysis Set
17.2	Hematology: Monocytes, Eosinophils, and Basophils	Safety Analysis Set
17.3	Hematology: Hemoglobin, Hematocrit, Platelets, and MCV	Safety Analysis Set
18	Coagulation and Thyroid Function: INR, PT, APTT	Safety Analysis Set
19.1	Chemistry: Albumin, Alkaline Phosphatase, ALT, AST, Total Bilirubin, and Direct Bilirubin	Safety Analysis Set
19.2	Chemistry: Serum Creatinine, Estimated GFR (Cockcroft-Gault)	Safety Analysis Set
19.3	Chemistry: Lipase, Potassium, Sodium, and Glucose	Safety Analysis Set
20	CD4 T-Lymphocyte Absolute Count and % and HIV RNA (copies/mL)	Safety Analysis Set
21	Height, Weight, BMI and Vital Signs	Safety Analysis Set
22.1	Subjects with HIV Virologic Rebound	Safety Analysis Set
22.2	HIV RNA, Change and Percent Change from Baseline by Visit for Subjects Not on ARV at Baseline	Safety Analysis Set

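### Serum phosphorus is missing from the scheduled chemistry panel, although the protocol reports Grade 3-4 low phosphorus, with and without RBV, in an earlier study of GS-7977 plus daclatasvir

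*Combined protocol and SAP*

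**What the plan says.** **Earlier data.** Protocol Section 1.3.4 describes Study AI444-040. One of its regimens was "GS-7977 400 mg QD + DCV 60 mg QD + ribavirin for 24 weeks"; the other two combined the same two antivirals without RBV, one of them after a week of GS-7977 alone. In Section 1.3.4.1 the list of Grade 3-4 laboratory findings in the RBV-treated patients ends with "lymphopenia and low serum phosphorus—all of which occurred in patients who received RBV". The next sentence turns to the groups without RBV: "Grade 3-4 laboratory abnormalities reported in the RBV-sparing treatment groups were low phosphorus and elevated cholesterol". Neither sentence gives a count.

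**What this trial measures.** The chemistry list in Section 6.4.1 consists of ALT, AST, "Albumin, Alkaline phosphatase, Creatinine, Total Bilirubin (reflex to Direct Bilirubin), Glucose, Lipase, Potassium, Sodium", FibroTest, APRI and GGT. The additional tests in that section are a urine drug screen, HbA1c, TSH and CD4. The visit tables in Appendix 2 schedule chemistry as a block and add no phosphorus.

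**How results are graded and shown.** Appendix 3 has an adult hypophosphatemia row (Grade 3: 1.0 to <1.5 mg/dL; Grade 4: <1.0 mg/dL). SAP Tables 19.1 and 19.2 summarise treatment-emergent graded abnormalities on that scale. Phosphorus is not among the numeric summaries in SAP Section 7.2.1, nor in Listings 19.1 to 19.3, the last of which is titled "Chemistry: Lipase, Potassium, Sodium, and Glucose".

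**The concern.** Low phosphorus is the only Grade 3-4 abnormality that Section 1.3.4.1 names both with and without RBV, so it is the one finding there that did not depend on RBV. The other findings in the RBV list are covered by this trial's hematology and chemistry panels. Phosphorus is not.

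Safety is a primary objective, and it is to be judged from the accumulated safety data. An analyte that is never scheduled has no baseline, no follow-up and no grade, so the study report could give no rate for it in HIV/HCV co-infected subjects. Adverse event reporting is only a partial substitute: Section 8.5 says that laboratory abnormalities are not normally recorded as adverse events unless they meet further conditions.

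**Working it through.** The plan states no figure on this point, so there is nothing to reproduce. The check compares the sections and then sizes the gap.

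**1. Grade 3-4 findings in Section 1.3.4.1 against the panel in Section 6.4.1**

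| Finding | With RBV | Without RBV | Assayed at scheduled visits here |
|---|---|---|---|
| Anemia | named | not named | yes (hemoglobin) |
| Raised glucose | named | not named | yes (glucose) |
| Lymphopenia | named | not named | yes (WBC differential) |
| Low phosphorus | named | named | **no** |
| Raised cholesterol | not named | named | no |

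Scheduled phosphorus measurements per subject: 0.

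**2. What measurement could show.** Planned N = 230 (protocol synopsis, Section 3.1). The documents give no rate, so the rate p is an assumption, taken over 0.5-3%. Expected cases = 230 × p. Chance of at least one case = 1 − (1 − p)^230.

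| Assumed p | Expected cases | Chance of at least one |
|---|---|---|
| 0.5% | 1.15 | 68% |
| 1% | 2.3 | 90% |
| 2% | 4.6 | 99% |
| 3% | 6.9 | 99.9% |

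Setting the chance to 95% gives p = 1 − 0.05^(1/230) = 1.3%. Rates at or above this would very probably show at least one case.

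The documents offer one loose anchor for the range. Section 1.3.4.1 implies at least one case with RBV and at least one without. If its safety data cover the 88 patients of the initial phase (44 + 44, Section 1.3.4), that is at least 2/88 = 2.3%. If the expansion groups are included, the denominator is larger and the floor lower. The figure belongs to a regimen with daclatasvir and is not an estimate for this trial.

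**3. Workload.** Chemistry is drawn at Screening, Day 1, Weeks 1, 2, 4, 6, 8, 10 and 12, and post-treatment Week 4, which makes 10 samples. The 24-week groups add Weeks 16, 20 and 24, which makes 13. With equal enrollment of naive and experienced genotype 2/3 subjects, about 57 are treated for 12 weeks and 230 − 57 = 173 for 24 weeks. So 57 × 10 + 173 × 13 = 570 + 2,249 = 2,819 results. This ignores screen failures and early discontinuation.

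**The case against.** **The signal is thin.** It rests on two uncounted mentions in preliminary data from one external study. Every group received daclatasvir and none was without GS-7977. A reader might infer that low phosphorus is an established GS-7977 toxicity. The documents do not support that, and Section 1.9 says that no safety issue specific to GS-7977 has been identified. This stands: attribution is open.

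**Other studies in the protocol are reassuring.** GS-US-334-0131 saw no Grade 3 or 4 laboratory abnormalities (Section 1.3.1.2), and P7977-1910 saw no new safety signals in co-infected subjects (Section 1.3.2.2). This counts, but only so far. GS-7977 was given as single doses in the first and for 7 days in the second, and neither summary says whether phosphorus was assayed. The GS-7977 + RBV arms of QUANTUM had no Grade 3 or 4 adverse events (Section 1.3.5.1), but that statement is about adverse events rather than laboratory values.

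**A case could still surface.** Assessments at unscheduled visits are left to the investigator (Section 6.2.5). Section 8.5 requires an abnormality to be recorded as an adverse event if it needs intervention, leads to interruption or discontinuation of study drug, or comes with symptoms and meets the event definition. This stands. What is lost is systematic measurement, not every possibility of detection.

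**Tables 19.1 and 19.2 would not report a false zero.** SAP Section 7.2.2.3 uses subjects with non-missing values of the parameter as the denominator. An unmeasured analyte would have no denominator and would simply not appear.

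**Tenofovir.** All the listed regimens start from "emtricitabine/tenofovir plus" a third agent, and a reader might infer a raised risk of phosphate loss that a Screening-only urinalysis would miss. No section links tenofovir or urinalysis to phosphate, so the point does not rely on either.

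**Why phosphorus alone?** Raised cholesterol is also unmeasured. It is named only in groups without RBV, however, and every subject here is assigned RBV. Appendix 3 grades cholesterol on fasting samples, whereas subjects here take the morning dose with food before the visit. The unused hypophosphatemia row proves little by itself, because Appendix 3 is a general scale that also grades other unmeasured analytes, such as calcium and magnesium.

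**Unseen sources.** The panel may rest on the Investigator's Brochure, which is not available here.

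**Conclusion.** The point holds as a gap in measurement. The protocol reports Grade 3-4 low phosphorus with and without RBV in patients given GS-7977 plus daclatasvir, and this trial schedules no phosphorus assay. The Appendix 3 grades therefore cannot be applied systematically. It is a design choice that can be improved cheaply. It is not a contradiction in the plan or evidence of harm.

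The size cannot be taken from the documents. Under assumed rates of 0.5-3%, measuring 230 subjects would be expected to find between about 1 and 7 cases. The calculation assumes that all 230 are measured and that cases are independent. The gain would be a descriptive rate and individual identification; in a study without a control arm it would not settle cause.

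**What to change.** Add serum phosphorus to the Chemistry list in protocol Section 6.4.1, run on the chemistry sample already drawn at each scheduled visit. Add it to SAP Listing 19.3. SAP Tables 19.1 and 19.2 can then grade it against baseline using the existing Appendix 3 row, with the Screening and Day 1 samples supplying the baseline. The SAP covers only the EMEA 120-day response and AASLD analysis, so the same addition should be carried into the specification for the final report.

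The cost is the assay for about 2,800 results and review of incidental mild values. No extra visit or blood draw is needed, and no dose or stopping rule changes. If the sponsor has grounds elsewhere for leaving phosphorus out, a sentence in the protocol giving them would also close the gap in reasoning, though not the gap in data.
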